11.1.6 Visit 14 (Week 4S [\pm 5 days]) / Early Termination Visit

The following procedures will be conducted at this visit:

1. Record any AEs (query subject and their parent/legal guardian "Are there any changes in your health since the last visit?").
2. Record local skin reaction scores reported by the subject and parent/legal guardian.
3. Review concomitant medications.
4. Clip the toenails.
5. Measure the target great toenail growth since the Baseline Visit (distance from proximal nail fold to transverse notch). If the most recently applied notch has grown out or has been clipped off, inscribe a new notch adjacent to the proximal nail fold.
6. Conduct the investigator's assessment of the target great toenail, with a determination of the percentage of toenail affected with disease. Measure the distance from the proximal nail fold to the proximal onychomycotic border.
7. Perform the investigator's assessment of the nontarget toenails for the presence or absence of onychomycosis.
8. Obtain specimens from the target great toenail for fungal culture and KOH examination and send to the mycology central lab per instructions provided in the laboratory manual.
9. Take close-up photographs of the target great toenail. The first photograph will be taken after toenail clipping. After that photograph is taken, the investigator/evaluator will use a fine tipped marker to outline the area affected on the target great toenail. When the marker ink has dried, a second close-up photograph will be taken.
10. Conduct an abbreviated physical examination (excluding urogenital/reproductive systems).
11. Measure height and weight
12. Obtain vital sign measurements. Vital signs will be measured after the subject is seated for at least 5 minutes, and include systolic and diastolic blood pressure, pulse rate, respiratory rate, and oral body temperature.
13. Collect the diary and study drug bottle from the subject and/or parent/legal guardian. Weigh the used bottle of the study drug. Record the number of missed doses from the subject diary and review compliance with the subject and parent/legal guardian.
14. Conduct a urine pregnancy test on FOCBP subjects (if positive test result, the subject should return for Visit 15 [Week 52])

15. Collect blood and urine samples for routine safety laboratory analysis (hematology, serum chemistry, and urinalysis). Process and ship the samples to the central safety laboratory per instructions provided in the laboratory manual.
16. If this is the Early Termination Visit, record the reason for subject discontinuation from the study and complete the Week 48 eCRF. If this is not an Early Termination Visit, the subject should be scheduled to return for the Visit 15 (Week 52) study visit.

11.1.7 Visit 15 (Week 52 [\pm 5 days]) Post-Treatment Follow-up Visit / Study Exit

For all subjects who continue through the Week 48 visit, this visit should occur 4 weeks after the last treatment visit.

The following procedures will be conducted at this visit:

1. Record any AEs (query subject and their parent/legal guardian, "Are there any changes in your health since the last visit?").
2. Record local skin reaction scores reported by the subject and parent/legal guardian.
3. Review concomitant medications.
4. Clip the toenails.
5. Measure the target great toenail growth since the Baseline Visit (distance from proximal nail fold to transverse notch).
6. Conduct the investigator's assessment of the target great toenail, with a determination of the percentage of toenail affected with disease. Measure the distance from the proximal nail fold to the proximal onychomycotic border.
7. Perform the investigator's assessment of the nontarget toenails for the presence or absence of onychomycosis.
8. Obtain specimens from the target great toenail for fungal culture and KOH examination and send to the mycology central lab per instructions provided in the laboratory manual.
9. Take close-up photographs of the target great toenail. The first photograph will be taken after toenail clipping. After that photograph is taken, the investigator/evaluator will use a fine tipped marker to outline the area affected on the target great toenail. When the marker ink has dried, a second close-up photograph will be taken.
10. Conduct a urine pregnancy test on FOCBP subjects.
11. Exit the subject from the study.

11.1.8 Unscheduled Visits

Additional visits may be scheduled, as necessary, to ensure the safety and well-being of subjects. All additional exams should be fully documented in the source documents and on Unscheduled Visit eCRFs, as appropriate. Visits intended to fulfill scheduled visit requirements that fall outside the designated scheduled visit range, are not unscheduled visits. In these cases, the visit data will be collected and transcribed to the appropriate scheduled visit eCRF.

11.1.9 Missed Visits

If a subject misses any scheduled visit and cannot be seen prior to the start of the allowed visit range for the next scheduled follow-up visit, the visit is considered missed.

11.1.10 Subject Completion

A subject has completed the study when Visit 15 (Week 52) has been completed and the subject has been exited from the study. Subjects who require further follow-up for an AE following completion of the study will be followed according to Section 12.0.

11.2 Study Evaluations

11.2.1 Local Skin Reactions

Tolerability will be evaluated through assessment of local redness, swelling, burning, itching, and vesication in the selected treatment areas on the toes. Each sign or symptom is to be reviewed with the subjects and their parents/legal guardians after the first application of the study drug at the Baseline Visit and at each follow-up visit through Week 52. The subjects and their parents/legal guardians should assess each reaction based on the worst reaction experienced since the prior visit using the following scales:

Reaction	Score
Redness, Swelling	0 = None 1 = Mild 2 = Moderate 3 = Severe
Burning, Itching, and Vesication	Yes or No

Occurrence of vesication will always be reported as an AE. Any other sign or symptom will be reported as an AE only if it requires concomitant therapy or results in a temporary interruption or permanent discontinuation of the study drug due to discomfort.

11.2.2 Clinical Laboratory Tests

Blood and urine samples will be collected for routine safety laboratory tests (hematology, serum chemistry, and urinalysis) at the Screening and Week 48/Early Termination visit. Any subject with a screening laboratory abnormality that is determined by the investigator to be clinically significant must be approved for inclusion in the study by the medical monitor. All results will be reported, including abnormal results. Clinically significant changes in lab results from Screening, in the opinion of the investigator, should be reported as AEs. Clinically significant changes present at Week 48/Early Termination are to be followed to resolution or until clinically stable as determined by the investigator. If an AE should require laboratory testing, the results of the test must be obtained by the investigational center and filed in the subject's documentation.

Materials for sample collection will be provided to the investigational centers by the sponsor or central laboratory. Instructions for processing and shipping samples to the central laboratory are contained in the study laboratory manual.

For all FOCBP, urine pregnancy testing will be performed at the Screening and Baseline Visits, as well as at each subsequent study visit. FOCBP is defined as any female subject who has experienced menarche. The results at the Screening and Baseline Visits must be negative for a subject to enter the study. Materials for pregnancy testing will be provided to the investigational centers by the sponsor or central laboratory.

11.2.3 Vital Sign Measurements

Measurement of vital signs will be performed at the Baseline Visit, as well as at Weeks 12, 24, 36, and 48/Early Termination. After the subjects have been sitting for at least 5 minutes, systolic and diastolic blood pressures, pulse rates, respiration rates, and oral temperatures will be recorded.

11.2.4 Physical Examinations

An abbreviated physical examination will be performed at the Baseline Visit and at Week 48/Early Termination. Height and weight will be measured at the Baseline Visit and at the Week 48/Early Termination Visit.

11.2.5 Efficacy for Assessing Treatment Compliance and Safety

Efficacy assessments will be performed throughout the study. The efficacy analyses will be based on microscopic examination and mycological culture results for the target great toenail, the percent involvement of the target great toenail, the length of the unaffected part of the target great toenail, the growth of the target great toenail, and the number of affected nontarget toenails.

Investigators/evaluators will be trained by the sponsor to ensure consistency across investigational centers regarding toenail clipping, evaluations and measurements, as well as collection of sufficient material for KOH examinations and fungal cultures. Evaluators must be pre-approved by the sponsor and must have appropriate documented experience and training, or have a waiver obtained from the sponsor based on experience (or through additional training organized by the sponsor).

Every effort should be made to have the same sponsor-approved evaluator perform the target great toenail assessments and measurements for a particular subject at the Baseline Visit and each follow-up visit.

11.2.5.1 KOH Examination and Fungal Culturing

The KOH examination and fungal culturing of toenail scraping and subungual debris will be performed for study-eligible great toenail(s) at the Screening Visit and for the target great toenail only (as determined at the Baseline Visit) at Weeks 12, 24, 36, 48/Early Termination, and 52 (the

4-week post-treatment follow-up) study visits. At the Screening visit, specimens for KOH and fungal cultures are obtained from study-eligible great toenails at this visit and sent to the central mycology laboratory for testing.

Toenail specimens will be taken by clipping the toenail to the point of attachment (removing unhealthy nail) and obtaining any crumbling subungual debris from under the distal edge of the target great toenail using a disposable curette. All target great toenail plate clippings and "distal" subungual debris should be discarded. Only the soft nail bed keratin beneath the clipped edge of the nail should be collected and used as a specimen for both the KOH examination and the fungal culture. Careful specimen collection in this manner will minimize toenail specimen contaminants and maximize dermatophytic pathogen isolation.

Materials for sample collection will be provided to the investigational centers by the sponsor or central mycology laboratory. Instructions for processing and shipping samples to the central laboratory are contained in the study laboratory manual.

11.2.5.2 Target Great Toenail Assessments

The percent of the affected toenail area and healthy (unaffected) toenail measurements for the target great toenail will be evaluated by the investigator/evaluator at the Screening and Baseline Visits, and at Weeks 12, 24, 36, 48/Early Termination, and 52 (the 4-week post-treatment follow-up) study visits.

Percent of Affected Target Great Toenail Area

The affected area of the toenail will be estimated as the percent of toenail area (nail and nail bed) involved (the distal margin for determining area will be the distal groove after the toenail has been clipped).

Healthy (Unaffected) Target Great Toenail Measurement and Growth

The healthy (unaffected) toenail measurement will be defined as the distance (in mm) between the proximal nail fold and a transverse line on the healthy part of the toenail immediately proximal to the nail infection. At each evaluation, this distance will be measured from the proximal nail fold to the proximal onychomycotic border.

Toenail growth will be measured by inscribing a transverse notch in the nail of the target great toenail adjacent to the proximal nail fold at the center of the nail at the Baseline Visit, and measuring nail growth from that point forward. At every subsequent visit, the distance (in mm) between the proximal nail fold and the notch will be measured and recorded. The notch should be enhanced as needed at subsequent visits to allow continued measurement of toenail growth over the course of the study. If the initially applied notch inscribed at the Baseline Visit has grown out or is clipped away, inscribe a new notch in the toenail adjacent to the proximal nail fold, and continue with measurements using the new notch.

11.2.5.3 Nontarget Toenail Assessment

An assessment of both feet will be made for assessing the presence or absence of onychomycosis of nontarget toenails at the Screening, Baseline, Weeks 12, 24, 36, 48/Early Termination, and 52 (the 4-week post-treatment follow-up) study visits. All nontarget toenails will be assessed for the presence or absence of onychomycosis. Subjects in the PK subset must present with onychomycosis on at least 4 toenails besides the great toenails.

11.2.6 Evaluation of Pharmacokinetics

The PK assessments will be performed on a subset of the study population who will receive treatment under maximal use conditions for 28 days. Plasma samples for determination of efinaconazole and metabolite levels will be collected at the following time points:

- Visit 3 (Day 28): Predose (after all Day 28 procedures are completed). Study drug must be applied within 1 hour after the predose sample is collected. Samples are then collected at 2 (\pm 5 min), and at 4 (\pm 5 min), and at 12 (\pm 15 min) hours postdose.
- Visit 3A (Day 29): 24 (\pm 30 min) hours after Day 28 study drug application.

Materials for sample collection will be provided to the investigational centers by the sponsor or central laboratory. Instructions for processing and shipping samples to the bioanalytical laboratory are contained in the study laboratory manual.

11.2.7 Photography

At all investigational centers, close-up photographs of the target great toenail will be taken at the Baseline, Weeks 24, 48/Early Termination, and 52 (the 4-week post-treatment follow-up) study visits. One photograph will be taken after toenail clipping. After the first photograph has been taken, the investigator/evaluator will use a fine tipped marker to outline the area affected on the target great toenail. After the ink has dried, a second photograph will be taken. The collected photographs will be used for documentation purposes only and will not be used for determinations of eligibility, efficacy, or any study-related activities. Before photographs are taken, the study subject and their parent(s)/legal guardian(s) must consent/assent to photography. If the photography consent/assent is declined, the subject may still participate in the study.

11.3 Definition of Adverse Events

An AE is any untoward medical occurrence in a subject or clinical investigation subject administered a medicinal product and which does not necessarily have a causal relationship with the study drug. Thus, AEs include any unfavorable and unintended illness, sign, symptom, clinically significant laboratory test abnormality, or disease temporally associated with the use of a medicinal product that has appeared or worsened during the course of the clinical study, regardless of causal relationship to the study drug(s) under study. The collection of nonserious

AEs and serious adverse events (SAEs) should begin following the subject's completion of the consent/assent process to participate in the study.

11.3.1.1 Definition of Serious Adverse Events

All AEs will be assessed as either serious or nonserious. An SAE or serious adverse reaction is defined as any untoward medical occurrence that at any dose:

- Results in death.
- Is immediately life threatening, (the term "life threatening" in the definition of "serious" refers to an event in which the subject is at risk of death at the time of the event; it does not refer to an event which hypothetically might have caused death if it were more severe).
- Requires in subject hospitalization or prolongation of existing hospitalization (hospitalization for elective surgery for a baseline condition is not considered an AE).
- Results in persistent or significant disability/incapacity (permanent or substantial disruption of a person's ability to conduct normal life functions).
- Is a congenital anomaly/birth defect.
- Is a medically important event that may not be immediately life threatening or result in death or hospitalization, but may jeopardize the subject and may require medical or surgical intervention to prevent one of the above listed outcomes.

Important medical events that may not have resulted in death, be life-threatening, or require hospitalization may be considered an SAE when, based upon appropriate medical judgment, they may jeopardize the subject and may require medical or surgical intervention to prevent one of the outcomes listed in this definition. Examples of such medical events include allergic bronchospasm requiring intensive treatment in an emergency room or at home, blood dyscrasias or convulsions that do not result in inpatient hospitalization, or the development of drug dependency or drug abuse.

Hospitalization is a criterion for assessment of seriousness. To qualify as serious under the criteria of "hospitalization," a hospital admission of at least a 24-hour period is required. If a subject is retained in the emergency room greater than 24 hours, but not admitted for medical care, these cases should be evaluated individually, as criteria such as "medically significant" may also apply.

Hospitalization without a medical AE should not be considered either serious or an AE. Examples include:

- Admission for treatment of a pre-existing condition not associated with the development of a new AE or with worsening of the pre-existing condition (eg, for work-up of persistent pre-treatment lab abnormality).
- Hospitalization for a purpose unrelated to the study (eg, "planned" or elective surgery scheduled prior to study participation) would not ordinarily need to be reported, unless a complication occurred which otherwise caused prolongation of this hospitalization.
- Protocol-specified admission or procedure (eg, cataract surgery required by a study protocol; or overnight stay for monitoring due to protocol required surgery, *with no associated SAE or complication necessitating prolonged stay*)
- Social admission (eg, social hospitalization for purposes of respite care)

Note: A spontaneous abortion will be considered an SAE, and must be reported to the sponsor within 24 hours of your awareness of the event.

11.3.1.2 Assessment of Severity

The severity assigned to an AE should be determined by the maximum severity of the AE. The categories described below should be used to estimate the severity of AEs:

- Mild: Transient or mild discomfort; no limitation in activity; no medical intervention/therapy required.
- Moderate: Mild to moderate limitation in activity; some assistance may be needed; no or minimal medical intervention/therapy required.
- Severe: Marked limitation in activity; some assistance usually required; medical intervention/therapy required; hospitalization or prolongation of current hospitalization possible; may be incapacitating or life threatening.

11.3.1.3 Assessment of Causality

The investigator should assess the relationship of the AE, if any, to the study drug as either "Related" or "Not Related".

- **Related:** There is at least a reasonable possibility that the AE/SAE is related to the study drug. Reasonable possibility means that there is evidence to suggest a causal relationship between the drug and the AE.
- **Not Related:** There is little or no reasonable possibility that the AE/SAE is related to the study drug. This assessment implies that the AE/SAE has little or no temporal relationship to the study drug and/or a more likely or certain alternative etiology exists.

The following should be taken into account when assessing AE/SAE causality:

- Positive temporal relationship to study drug, such as if the study drug was withdrawn and the SAE resolved or the event recurred after re introduction.

- If there is a reasonable possibility that the AE is associated with an underlying or concomitant illness.
- Possible association with previous or concomitant therapy.
- No temporal relationship to the study drug and/or a more likely alternative etiology exists.
- If the AE is directly related to study procedures or there is a lack of efficacy.

11.3.1.4 Procedures for Reporting Adverse Events and Serious Adverse Events

The period of observation for collection of AEs extends from the time the subject and parent/legal guardian gives informed consent/assent until the last study visit or discontinuation from the study. The first concern will be the safety of the subject, and appropriate medical intervention will be made.

The Investigator or designee will elicit reports (ie, via direct questioning, observation, clinical evaluation) of AEs from the subject at each study visit and record all AEs. The Investigator will document the dates of onset, progress, outcome, and resolution of such AEs. The Investigator will also provide an assessment of all AEs as to the severity, causal relationship to study drug, and causal relationship to study protocol.

It is the investigator's responsibility to document all AEs that occur during the study. The AEs should be documented as a single medical diagnosis. When this is not possible, the AE should be documented in terms of signs and/or symptoms observed by the investigator or reported by the subject and/or their parent/legal guardian at each study visit.

All AEs occurring after the subject and their parent/legal guardian signs the assent/informed consent through the last study visit must be reported, regardless of whether or not the AEs are considered drug-related. All AEs, whether in response to a query, observed by the study site personnel, or reported spontaneously by the subject and/or their parent/legal guardian, will be recorded.

At each visit during the study, the subject will be assessed for the occurrence of new and ongoing AEs. Cutaneous tolerability signs and symptoms that result in the subject's requiring a concomitant therapy or discontinuation from the study will be reported as an AE. The following data will be collected on all AEs and recorded on the appropriate eCRF:

- Event name (diagnosis preferred, if unknown, record the signs/symptoms).
- Onset date and end date.
- Maximum intensity (severity).
- Seriousness.

- Action taken regarding study drug.
- Corrective treatment, if given.
- Outcome.

In addition, the investigator's assessment of causality will be recorded.

Any SAE must be reported to the Sponsor, independent of the circumstance or suspected cause, within 24 hours from the time the event was reported to the Investigator. All SAEs experienced from the date of consent through at least 30 days after the last dose of study drug must be reported to the Sponsor regardless of the relationship to the study drug or the protocol. For events occurring beyond the minimum 30-day period after the last dose of study drug, or for any timeframe afterward deemed medically significant, only SAEs considered related to the study drug should be reported promptly to the Sponsor.

Within 24 hours of notification the Investigator will fax or email a completed Serious Adverse Event Report to the Sponsor:

MedTrials Safety:

Fax: [REDACTED]

**Please follow up with an email notification to
[REDACTED] to confirm the faxed submission.

Investigators should not wait to receive additional information to document the event before notifying the sponsor of an SAE. If only limited information is initially available, follow-up reports are required. If the Investigator becomes aware of any new information regarding a SAE (ie, resolution, change in condition, or new treatment), a new SAE Form must be completed and faxed/mailed to the Sponsor within 24 hours. The original SAE form is not to be altered. The report should be marked as a "follow-up report" and describe whether the event has resolved or continues and how the event was treated. Additional relevant information such as hospital records and autopsy reports should be provided to the sponsor as soon as they are available.

Should the investigator become aware of an SAE (regardless of its relationship to investigational product) that occurs within 30 days after stopping the study drug, the SAE must be reported in accordance with procedures specified in this protocol.

The investigator should take all appropriate measures to ensure the safety of the subjects, notably he/she should follow a subject with an SAE until the event has resolved or the condition has stabilized. This may imply that follow-up will continue after the subject has left the study, and that additional investigations may be requested by the sponsor.

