^q The subject or their parent/legal guardian will apply the first dose of study drug in the investigational center, with guidance from study staff.

Visit	3					3A
Day (Week)	28 (4)					29 (4)
PROCEDURES	Predose	~1 h Following Pre-dose Sample	2 h (± 5 min)	4 h (± 5 min)	12 h (± 15 min)	24 h (± 30 min)
PK Subset - Collect Blood for Plasma Concentrations	X ^p		X	X	X	X

Visit	3			3A
Day (Week)	28 (4)			29 (4)
PK Subset - Study Drug Application		X ^q		

^p The predose blood sample is to be collected after all Day 28/Week 4 study procedures are completed.

^q Study drug application on Day 28/Week 4 will occur at the investigational center within 1 hour after collecting the predose blood sample.

This will be the last application of study drug to all 10 toenails for subjects in the PK subset. Post Day 28, subjects and their parents/legal guardians will be instructed to apply the assigned study drug to the subject's target great toenail and all other affected toenail(s). Subjects and their parents/legal guardians will be instructed to continue applying the study drug to the target great toenail for the entire treatment period, even if the disease clears and no affected area is observed on the target great toenail. If other affected toenails treated since baseline clear during the course of the study, subjects and/or their parents/legal guardians will be encouraged to continue treatment on those toenails for the duration of the study. In addition, if new toenails become infected during the study, the subject will be instructed to start treating the additionally affected toenail(s).

8 Selection and Withdrawal of Subjects

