The subjects will go home after Day 28, but will not apply study drug on the night of the Day 28 visit. All PK subjects in the 4-Week trial will return to the investigational center the following day (Day 29) for collection of a 24-hour post dose blood sample and exit the study. PK subjects that consented to the 52-Week trial will continue treatment with study drug to only the target great toenail and the other affected toenails and return to the investigational center at Weeks 8, 12, 16, 20, 24, 28, 32, 36, 40, 44, and 48, and a 4-week post-treatment follow-up visit (Week 52).

Safety will be assessed by reviewing the occurrence of AEs and local skin reactions, assessing vital sign measurements and abbreviated physical examination findings, and noting any additions or changes in concomitant medication uses. Blood samples will be collected at Screening, Week 4(Day 28) and Week 48 for routine safety laboratory evaluations (serum chemistry, hematology, and urinalysis); urine pregnancy tests will be obtained for all FOCBP at each study visit. Efficacy assessments will be performed throughout the study. The efficacy analyses will be based on microscopic examination and mycological culture results for the target great toenail, the percent involvement of the target great toenail, the length of the unaffected

part of the target great toenail, the growth of the target great toenail, and the number of affected nontarget toenails.

Note that growth of the target great toenail will be measured by inscribing a transverse notch, at the center of the toenail, in the toenail adjacent to the proximal toenail fold at Baseline and measuring toenail growth from that point forward. At every subsequent visit, the distance between the proximal toenail fold and the notch will be measured and recorded. A new notch will be inscribed in the toenail adjacent to the proximal toenail fold if the initially applied notch grows out during the course of the study.

A post-treatment follow-up visit will occur 4 weeks after the last treatment visit for each subject (ie, at Week 52). Subjects who discontinue from the study prior to Week 48 will complete the Week 48 study procedures.

Number of subjects planned:

Approximately 60 subjects total

Approximately 20 subjects in the PK subset

Diagnosis and criteria for inclusion:

1. Male or female subjects of any race, 6 to 16 years of age (inclusive) at Screening.

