Note: PK subjects exiting the study on Day 29 (consented to only the 4-Week trial), the following procedures will be conducted in addition to the procedures listed above.

11. Collect blood and urine samples for routine safety laboratory analysis (hematology, serum chemistry, and urinalysis). Process and ship the samples to the central safety laboratory per instructions provided in the laboratory manual.
12. Measure height and weight.
13. Conduct an abbreviated physical examination (excluding urogenital/reproductive systems).

For subjects in the PK subset at Visit 3 only:

- Collect a predose blood sample after all other study procedures are completed.
- Apply the study drug to all 10 toenails at the investigational center within 1 hour after collecting the predose blood sample.
- Collect postdose blood samples at approximately 2 hours (\pm 5 min), 4 hours (\pm 5 min), and 12 hours (\pm 15 min) after study drug application.
- Instruct the subject to return the following morning for their 24-hour blood sample (Visit 3A (Day 29). Subject will not dose on the evening of Day 28.

11.1.4 Visit 3A (Week 4, Day 29) - Additional Visit for Subjects in the PK Subset

The following procedures will be conducted at this visit:

1. Record any AEs (query subject "Are there any changes in your health?").
2. Record local skin reaction scores reported by the subject.
3. Review concomitant medications.
4. Collect a blood sample 24 hours (\pm 30 min) after study drug application at Visit 3.
5. Obtain 1 bottle of study drug and weigh the bottle, complete the label and drug log, and dispense the bottle to the subject and their parent/legal guardian. Review the new dosing instructions with the subject (application to only the target great toenail and to any other affected toenails) and provide a copy of new dosing instructions to the subject.
6. Dispense a new diary that includes the new dosing instructions.

Note: PK subjects who consented to only the 4 Week trial will exit the study on Day 29. Drug and subject diary will not be dispensed and urine pregnancy test will not be collected at this visit.

11.1.5 Schedule the PK subset subject (if consented to the 52-Week trial) for the next study visit. Visit 5 (Week 12 [\pm 5 days]), Visit S (Week 24 [\pm 5 days]), Visit 11 (Week 36 [\pm 5 days])

Visits are to be scheduled in reference to Visit 2 (Baseline).

The following procedures will be conducted at these visits:

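### SAEs must be reported to 30 days after the last dose, but no contact is scheduled to find them after 4-week PK subjects exit on Day 29 or after an Early Termination visit

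*Combined protocol and SAP*

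**What the plan says.** All references are to the current protocol version, the one that introduces the 4-week option for the PK subset.

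- **SAE window.** Section 11.3.1.4: "All SAEs experienced from the date of consent through at least 30 days after the last dose of study drug must be reported", whatever the suspected cause.
- **AE observation.** The same section runs general AE collection from consent "until the last study visit or discontinuation from the study", with events elicited at study visits.
- **After exit.** Section 11.3.1.4 makes later reporting depend on awareness: "Should the investigator become aware of an SAE (regardless of its relationship to investigational product) that occurs within 30 days after stopping the study drug", it is to be reported under the protocol's procedures.
- **4-week PK subjects.** Table 1, footnote s: "Study drug application on Day 28/Week 4 will occur at the investigational center within 1 hour after collecting the predose blood sample". Section 11.1.3: "Subject will not dose on the evening of Day 28". Section 11.1.4: "PK subjects who consented to only the 4 Week trial will exit the study on Day 29". Table 1 marks study exit at Visit 3A for this group and shows nothing after it.
- **Week 52 visit.** Section 11.1.7: "For all subjects who continue through the Week 48 visit, this visit should occur 4 weeks after the last treatment visit". Section 7.2 has the same restriction, and Section 11.1.6 schedules Week 52 only when the visit is not an Early Termination visit. The synopsis is unrestricted: "A post-treatment follow-up visit will occur 4 weeks after the last treatment visit for each subject".
- **Early terminators.** Section 8.3 asks them to return, where possible, for the Week 48 assessments. It does not say how long after the last dose.

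**The concern.** Safety is the first primary objective. The protocol sets a 30-day post-dose window for SAEs, but two groups leave scheduled observation before it ends. The change log says the 4-week option was added to meet the study timeline. That amendment added Day 28 laboratory tests, height and weight, and an abbreviated examination for these subjects. It added no contact after the last dose and left the 30-day rule in place.

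What is at stake is how the SAE tables are read. A row showing no SAEs among 4-week PK subjects would look like 30 days of follow-up per subject when one day was observed by plan. The PK population would also mix subjects observed for 1 day off drug with subjects observed for about 4 weeks. Separately, a site working from the synopsis and a site working from Section 11.1.7 could treat an early terminator differently.

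**Working it through.** The plan gives no coverage figure to reproduce, so this is calendar arithmetic. With D the day of the last dose and C the day of the last scheduled contact:

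uncovered days U = max(0, 30 − (C − D))

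**4-week PK subjects.** D = 28 (dosed in clinic, no evening dose) and C = 29. U = 30 − 1 = 29, and 29/30 = 96.7%. Section 12.8.6 allows Visit 3 within 1 day of Day 28 and puts Visit 3A one day after it, so D and C move together and U stays at 29 for dosing on Day 27, 28 or 29. Number affected: at most about 20 of 60 (33%), the whole PK subset.

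**Week 48 completers.** Week 48 is day 336 and Week 52 is day 364. Taking the last dose as falling on the Week 48 visit day (an assumption), C − D = 28, so U = 2 and 2/30 = 6.7%. Each visit has a ±5-day window counted from Baseline, so the interval can run from 28 − 10 = 18 days to 28 + 10 = 38 days.

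**Early terminators.** C is the Early Termination visit. The lag L = C − D is not specified, so a range is needed:

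| Lag L (days) | Uncovered days | Share of 30 |
|---|---|---|
| 0 | 30 | 100% |
| 7 | 23 | 77% |
| 14 | 16 | 53% |
| 15 | 15 | 50% |
| 28 | 2 | 7% |

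More than half the window is uncovered only if L is under 15 days.

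**Whole study.** There are 60 × 30 = 1,800 subject-days of window. With k 4-week PK subjects, e early terminators at zero lag (the worst case) and the rest completing:

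uncovered = 29k + 30e + 2(60 − k − e)

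- k = 0, e = 0: 120 days, 6.7%
- k = 10, e = 0: 290 + 100 = 390 days, 21.7%
- k = 20, e = 0: 580 + 80 = 660 days, 36.7%
- k = 20, e = 8: 580 + 240 + 64 = 884 days, 49.1%
- k = 20, e = 9: 580 + 270 + 62 = 912 days, 50.7%

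**The case against.** The strongest reply is that the protocol sets two windows on purpose: active AE collection to the last visit, and passive SAE reporting afterwards, triggered when the investigator learns of an event. That much stands. A reader might infer that the AE and SAE rules contradict each other; they do not, and an SAE that comes to light within 30 days is reportable. But the reply does not say how the investigator would learn of one. The gap is in ascertainment, not in the reporting rule.

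It can also be said that these subjects are not abandoned. Known SAEs are followed after the subject leaves, pregnancies are followed to term, and the synopsis has clinically significant Day 28 laboratory abnormalities followed up. So it would be too strong to say that later events surface only if the family calls. Still, these provisions follow something already detected, and Section 11.2.2 and Table 1 footnote l do not list Day 28 for laboratory follow-up.

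The synopsis conflict is fairly described as leftover text. Its sentence is tied to Week 52, the next sentence gives discontinuing subjects the Week 48 procedures, and the synopsis elsewhere has 4-week subjects exiting on Day 29. It needs an edit all the same.

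A reader might also infer that the group with least follow-up is the most heavily dosed. Per day that is so: 10 toenails plus a skin margin. Cumulatively it is not: at most 10 × 28 = 280 nail applications, against 336 for one nail over 48 weeks and 6 × 336 = 2,016 for six, ignoring nail size and the skin margin.

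**Conclusion.** The point holds for the two groups named. Followed exactly, the plan leaves 29 of 30 post-dose days without scheduled ascertainment in every 4-week PK subject, and between 7% and 100% of the window in early terminators for lags of 28 down to 0 days. SAE counts in these subjects may be incomplete. The gap should be corrected; it does not undermine the study as a whole.

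Four stronger readings are not supported:

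- **Most of the safety window is unobserved study-wide.** With all 20 PK subjects on the 4-week option and no early termination the figure is 36.7%. With all 20 on that option it passes half only with at least 9 early terminators at zero lag.
- **Twenty subjects are affected.** Twenty is a ceiling, because the split is not stated and the choice is offered to newly screened PK subjects.
- **Early terminators have no off-drug observation.** That assumes zero lag. They are asked to return for the full Week 48 assessments.
- **Pooled event rates are understated.** Nothing in the documents gives an SAE rate from which missed events could be estimated. Treatment of 4 versus 48 weeks is a larger source of non-comparability, and a follow-up call would not change it. Events are also tabulated separately for the PK and non-PK populations, and no hypothesis test is planned.

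**What to change.** 1. Add one telephone contact by existing site staff at least 30 days after the last dose, for 4-week PK subjects and early terminators, asking about SAEs. Extending non-serious AE collection to the same call is optional, since the 30-day rule covers SAEs only.
2. Reconcile the synopsis follow-up sentence with Sections 7.2, 11.1.6 and 11.1.7, so that all four say which subjects have the Week 52 visit.
3. If no call is added, state that SAE reporting after exit is passive, and give the observed off-drug follow-up by group next to the SAE tables.

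The cost is one short call per affected subject (at most about 20 PK subjects, plus early terminators) and an amendment sentence. Dosing, eligibility and visits are unchanged. Completers would remain nominally 2 days short of 30, which the report can state.
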